⁷ Age-dependent enrolment in each cohort needs to be considered when evaluating this inclusion criterion.

Confidentiality Statement

This document contains confidential information. It is intended solely for the use of the principal investigator, coinvestigators, staff, appropriate institutional review boards or ethical committees, and other required regulatory bodies.

AG019-T1D-101 CSP Final 9.0 11-Jun-2020

Inclusion Criteria	AC	СС
Ability and willingness of patient to participate fully in all aspects of this clinical study	Х	Х
Written informed consent obtained and documented (patient, parent, guardian as applicable)	Х	Х
Willingness to use a continuous glucose monitoring device and willingness to comply with the protocol defined glucose monitoring (note: this inclusion criterion does not apply to single dose patients)	Х	х
 Total bilirubin ≤1.0 x upper limit of normal (ULN) Aspartate aminotransferase (AST) or alanine aminotransferase (ALT) ≤1.5 x ULN ≥1,000 lymphocytes/μL ≥1,000 polymorphonuclear neutrophils (PMN)/μL ≥100,000 platelets/μL Hgb ≥10 g/dL Serum Creatinin ≤1.5 x ULN eGFR ≥60 mL/min/1.73m² INR ≤0.1 above upper limit of normal Absence of clinically significant age appropriate abnormalities on all other lab values, except for abnormalities directly attributable to T1D. 	Х	Х

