4.3. Exclusion Criteria

The below table provides an overview of all exclusion criteria which are required to be met for:

AG019 cohorts: column 'AC'

• Combination cohorts: column 'CC'

Exclusion criteria	AC	СС
Previous history of serious cytokine release syndrome to teplizumab or other humanized anti-CD3 monoclonal antibodies with no or minimal capacity to bind Fc receptors.		Х
Current use of any systemic antibiotics, except for the following: XXX	X	Х
Use of immunosuppressive or immunomodulatory therapies, including systemic steroids within 1 month prior to randomization	Х	Х
Participation in another investigational drug trial within 12 weeks prior to the first study drug intake and during participation in this study	Х	Х
History of recurrent infections, other autoimmune diseases, cardiac disease, malignancy, or any other (chronic) medical condition which, in the investigator's opinion, could compromise participant safety	Х	Х

Confidentiality Statement

Exclusion criteria	AC	СС	
Documented history of human immunodeficiency virus (HIV), Hepatitis Virus Type C (HCV), Hepatitis Virus Type B (HBV) infection	Х	Х	
Evidence of active infection with Epstein-Barr Virus (EBV) or cytomegalovirus (CMV)			
Positive result of SARS-Cov2 PCR test at screening or within 3 days before randomization			
Untreated hypothyroidism or active Graves' disease			
Evidence of any active infection with the exception of superficial skin infections		Х	
Vaccination with live virus or organism within 8 weeks prior to randomization (vaccination with killed virus within 2 weeks prior to randomization should be avoided as vaccine immunity may be compromised; however it is not exclusionary)		Х	
Evidence of active or latent tuberculosis (TB). All patients must be evaluated for TB; including history of TB or possible previous contact with TB. Appropriate screening tests (e.g. TST, TSPOT, QuantiFeron, or other appropriate tests) should be performed in all patients unless vaccinated with BCG.			
Administration of anti-CD3 antibody in past year	Х	Х	
Current therapy with any other anti-diabetic agents other than insulin (MDI, CSII or analogue). Current or planned therapy with experimental (i.e., unapproved) insulin. Patients on therapy for type 2 diabetes (e.g. metformin) should stop their therapy in order to be eligible for study participation.			
Use of medications known to influence glucose tolerance	Х	Х	
Daily use of systemic non-steroidal anti-inflammatory agents	Х	Х	

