- Liver function tests: alkaline phosphatase (ALP), AST, ALT, lactate dehydrogenase (LDH), total protein, albumin, total bilirubin
- Pregnancy tests for women of childbearing potential: serum (at screening), urine (at other visits the Sponsor can provide urine dip sticks if needed)
- Coagulation tests: INR
- Inflammatory: C-reactive protein (CRP)

Following additional blood parameters will be analysed at screening, and if no concerns are identified, these parameters will not require analysis at follow-up visits:

- Kidney function tests: uric acid, urea/blood urea nitrogen (BUN), creatinine, estimated glomerular filtration rate (eGFR)
- Cardiovascular tests: total cholesterol, triglycerides, high density lipoproteins (HDL), low density lipoproteins (LDL), very low density lipoproteins (VLDL - optional)
- Thyroid stimulating hormone (TSH)

Total bilirubin, AST, ALT, LDH, Complete Blood Count (CBC), and INR will be evaluated to verify the need to withhold teplizumab (or placebo) infusion before each (potential) teplizumab administration, as described in the Visit Schedule The drug infusion withholding criteria presented in Section 11.4.3.5 should be evaluated.

In addition to the above lab assessments to be analysed by the site's local lab, EBV/CMV/HCV/HBV/HIV monitoring assessments will be done. Potential reactivation will be assessed at regular intervals by viral serologies (IgG/IgM) and/or polymerase chain reaction (PCR) for viral load.

As part of the eligibility verification, the presence of one or more autoantibodies against beta cell antigens will be verified. If documentation of autoantibody positivity is found in the patient's medical file, the assessment does not have to be repeated at screening.

As part of the eligibility verification, all new patients will be tested for SARS-Cov2 at screening and within 3 days before the start of teplizumab/placebo infusions.

Confidentiality Statement

6.3.3Central lab assessments

6.3.3.1Pharmacokinetic Assessments

Following parameters will be assessed for analysis of systemic and local exposure to *L. lactis*:

- Presence of live L. lactis clinical strain bacteria in whole blood,XXX
- Measurable serum levels of hIL-10 and hPINS, XXX
- Presence of L. lactis clinical strain bacteria in fecal excretion, XXX

Throughout the study, blood and feces samples will be collected at regular intervals for analysis by the central laboratory, as described in the Visit schedule.

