- Urine pregnancy test (in women of childbearing potential)
- Blood sampling for mechanistic assessments (only for repeat dose patients in AG019 Cohorts
 2 and 4 and for patients in the combination cohorts)
- Record concomitant medications
- Record adverse events
- Placement of CGM device, training of patient on how to place the CGM device at home
- ePRO review including insulin use and hypoglycemic events
- Blood sampling for local lab (hematology, full chemistry, INR)
- Evaluation of drug infusion withholding criteria (only for Combination Cohorts)
- Administer first dose of AG019/placebo (for combination cohorts, randomized treatment should be respected)
- First teplizumab/placebo (randomized treatment should be respected)

For patients enrolled in the Repeat Dose AG019 cohorts, it is recommended to schedule the Day 1 visit on a Friday, to avoid having to schedule follow-up visits on weekend days.

For patients enrolled in the Combination cohorts, it is recommended to schedule the Day 1 visit on a Monday, to avoid study drug infusions in 2 consecutive weekends.

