11.4.3.5 Teplizumab Withholding in an Individual Patient During the 12-Day Treatment Period

Total bilirubin, AST, ALT, LDH, Complete Blood Count (CBC), and INR will be evaluated to verify the need to withhold teplizumab (or placebo) infusion before each (potential) teplizumab administration, as described in the Visit Schedule (Appendix A).

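### The liver entry criterion joins AST and ALT with 'or', so as written a patient with one clearly raised enzyme meets it; the wording should require each enzyme to be within the limit

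*Protocol*

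**What the plan says.** Protocol section 4.2 lists the laboratory entry limits in one row, marked for both AG019 and combination cohorts. The transaminase line is "Aspartate aminotransferase (AST) or alanine aminotransferase (ALT) ≤1.5 x ULN". The row ends with a catch-all: "Absence of clinically significant age appropriate abnormalities on all other lab values", apart from abnormalities directly attributable to T1D.

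Section 4.3 excludes patients, in both cohort types, for several named histories and for "any other (chronic) medical condition which, in the investigator's opinion, could compromise participant safety". No enzyme level is attached to it.

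After screening, section 7.3.2 lists for all repeat dose patients, before first dosing on Day 1, "Blood sampling for local lab (hematology, full chemistry, INR"). The same list contains "Evaluation of drug infusion withholding criteria (only for Combination Cohorts"). Section 11.4.3.5 describes what that evaluation uses: "Total bilirubin, AST, ALT, LDH, Complete Blood Count (CBC), and INR will be evaluated to verify the need to withhold teplizumab (or placebo) infusion". Section 11.4.3.4, on stopping AG019 in one patient, names sepsis, withdrawal of consent and pregnancy.

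**The concern.** The primary objective is safety, AG019 has not been given to humans before, and patients are enrolled from age 12. An entry limit on transaminases is there to ensure that patients start without a material elevation. If one enzyme within range is enough, the other has no numeric cap at entry.

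Two things are at stake. The first is that a patient could be dosed with an elevation that the criterion was presumably written to keep out. The second is consistency: sites in two countries may read the line differently, so that the same patient is eligible at one site and a screen failure at another. A smaller, analytical matter is that SAP section 6.3.9 plots mean and median AST per cohort, and the groups are very small.

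**Working it through.** The plan gives no figure for this point, so there is none to reproduce. The check reads the criterion as a logical condition and then follows AST and ALT through the rest of the plan.

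**1. The criterion as a condition.** The limit is 1.5 x ULN (section 4.2). The enzyme values below are illustrative.

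| AST (x ULN) | ALT (x ULN) | Met as written ('or') | Met if both are required |
|---|---|---|---|
| 1.0 | 1.0 | yes | yes |
| 1.0 | 4.0 | yes | no |
| 4.0 | 1.0 | yes | no |
| 4.0 | 4.0 | no | no |

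The two readings differ exactly where one enzyme is raised. The literal reading also matches usage elsewhere in the same table: the glucose criteria for diagnosis and the contraception options are joined by 'or', and any one of them suffices.

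**2. Other eligibility lines.**
- The catch-all is confined to other laboratory values. AST and ALT have their own line, so it does not clearly reach them.
- The bilirubin and INR limits in the same row are tight but do not cap a transaminase.
- The section 4.3 exclusion quoted above depends on the investigator's opinion of a medical condition. Documented hepatitis B or C is excluded separately, but that concerns a cause and not an enzyme level.

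**3. Later tests in the AG019 cohorts.**
- Section 6.3.2 places both enzymes in the general local panel: "Liver function tests: alkaline phosphatase (ALP), AST, ALT, lactate dehydrogenase (LDH), total protein, albumin, total bilirubin". The screening-only list that follows ("Following additional blood parameters will be analysed at screening, and if no concerns are identified, these parameters will not require analysis at follow-up visits") covers kidney tests, lipids and TSH.
- Repeat dose patients have local laboratory draws on Day 1 before dosing, on Days 4, 7, 12, 28 and 56, and at each follow-up visit (sections 7.3.2 to 7.3.4). That the Day 1 chemistry includes AST and ALT is an inference from section 6.3.2 and from the by-visit liver summaries in SAP section 6.3.9.
- Single dose patients (2 in each of 4 cohorts: 2 x 4 = 8) have laboratory tests at screening, which may be up to 28 days before dosing. None is listed at the Day 1 treatment visit, and the next is on Day 4 (section 7.2).

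**4. Rules that act on a later result.** The withholding evaluation applies to infusions in the combination cohorts only, and section 11.4.3.4 has no liver item. Section 11.4.3.3 acts on a proportion of patients with safety concerns and names no laboratory threshold. So the visible text has no AST or ALT threshold that acts on a later result in the AG019 cohorts. The enrollment-suspension criteria (11.4.3.2) and the withholding thresholds (11.4.3.5) are redacted, and Appendix A is not in the text.

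**5. Effect on a plotted mean (assumed values).** Suppose one patient enters at AST 3.0 x ULN and the others lie between 0.6 and 1.0 x ULN. Compared with a group wholly at the others' level, the mean rises by (3.0 − 1.0)/n to (3.0 − 0.6)/n:
- n = 6: 2.0/6 = 0.33 to 2.4/6 = 0.40 x ULN
- n = 4: 2.0/4 = 0.50 to 2.4/4 = 0.60 x ULN
- n = 2: 2.0/2 = 1.0 to 2.4/2 = 1.2 x ULN

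The documents give neither these values nor how often such a patient would present.

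**The case against.** The strongest reply is that the line is loosely worded but harmless. A single limit shared by two enzymes can be read as applying to each, and an investigator who saw one clearly raised enzyme could use the opinion-based exclusion. Surveillance after entry is also substantial. Abnormal results must be assessed for clinical significance (section 6.2), and the investigator and medical monitor review local laboratory results at set times (section 3.1). In the AG019 cohorts that includes a review before the next staggered patient is treated, and a DSMB review before the next cohort opens (section 3.2).

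Most of this stands. It disposes of a stronger reading that a reader might draw from the cohort-restricted withholding line, namely that AG019-cohort patients get no later liver check. That reading would cover all 8 single dose and 4 x 4 = 16 newly enrolled repeat dose patients, 24 in all. It is not supported: repeat dose patients have a pre-dose draw on Day 1 and regular draws afterwards, and single dose patients are tested on Day 4. What is absent from the visible text is a numeric rule, not a test. Only the 8 single dose patients lack a scheduled laboratory test between screening and dosing.

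A reader might also infer that the liver shift tables would be spoiled. They would not be. They classify each patient by baseline status, so an elevation at entry is shown as such. The SAP also gives differences from baseline, which remove a stable elevation, and medians alongside the means. If ALT is the raised enzyme, that elevation does not enter the AST figure.

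What the reply does not do is settle the criterion. Monitoring after entry does not decide who may enter, and an opinion-based exclusion does not supply the missing limit.

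**Conclusion.** The point holds as a wording defect in an eligibility criterion. Read literally, section 4.2 is met by a patient with one transaminase within 1.5 x ULN and the other at any level, and no other eligibility line clearly closes that gap. It applies to every cohort. It weighs somewhat more in the AG019 cohorts, where no AST or ALT threshold acting on later results is visible, and most for the 8 single dose patients.

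The size is modest. The documents do not show that the sponsor intends to admit such patients, and they give no basis for estimating how many would present. The effect on the analysis is confined mainly to plotted means in very small groups. The study is descriptive, with no statistical tests, so no inference is at risk.

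The conclusion rests on the visible text. A liver rule in the redacted criteria or in Appendix A would narrow the remark about later thresholds, but the entry line would still have two readings.

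**What to change.** The sponsor should confirm that the limit is meant to apply to both enzymes and reword the line in section 4.2 to: AST and ALT each ≤1.5 x ULN. The threshold is unchanged. The cost is one small edit to the inclusion table and at most a few more screen failures.

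If the sponsor in fact intends that one enzyme within the limit is enough, the protocol should say so explicitly, so that all sites apply the same rule. No action threshold for AG019 and no change to the visit schedule is proposed here; those are clinical decisions for the sponsor.

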4.3. Exclusion Criteria

The below table provides an overview of all exclusion criteria which are required to be met for:

AG019 cohorts: column 'AC'

• Combination cohorts: column 'CC'

Exclusion criteria	AC	СС
Previous history of serious cytokine release syndrome to teplizumab or other humanized anti-CD3 monoclonal antibodies with no or minimal capacity to bind Fc receptors.		Х
Current use of any systemic antibiotics, except for the following: XXX	X	Х
Use of immunosuppressive or immunomodulatory therapies, including systemic steroids within 1 month prior to randomization	Х	Х
Participation in another investigational drug trial within 12 weeks prior to the first study drug intake and during participation in this study	Х	Х
History of recurrent infections, other autoimmune diseases, cardiac disease, malignancy, or any other (chronic) medical condition which, in the investigator's opinion, could compromise participant safety	Х	Х

Confidentiality Statement

Exclusion criteria	AC	СС	
Documented history of human immunodeficiency virus (HIV), Hepatitis Virus Type C (HCV), Hepatitis Virus Type B (HBV) infection	Х	Х	
Evidence of active infection with Epstein-Barr Virus (EBV) or cytomegalovirus (CMV)			
Positive result of SARS-Cov2 PCR test at screening or within 3 days before randomization			
Untreated hypothyroidism or active Graves' disease			
Evidence of any active infection with the exception of superficial skin infections		Х	
Vaccination with live virus or organism within 8 weeks prior to randomization (vaccination with killed virus within 2 weeks prior to randomization should be avoided as vaccine immunity may be compromised; however it is not exclusionary)		Х	
Evidence of active or latent tuberculosis (TB). All patients must be evaluated for TB; including history of TB or possible previous contact with TB. Appropriate screening tests (e.g. TST, TSPOT, QuantiFeron, or other appropriate tests) should be performed in all patients unless vaccinated with BCG.			
Administration of anti-CD3 antibody in past year	Х	Х	
Current therapy with any other anti-diabetic agents other than insulin (MDI, CSII or analogue). Current or planned therapy with experimental (i.e., unapproved) insulin. Patients on therapy for type 2 diabetes (e.g. metformin) should stop their therapy in order to be eligible for study participation.			
Use of medications known to influence glucose tolerance	Х	Х	
Daily use of systemic non-steroidal anti-inflammatory agents	Х	Х	
Compromised GI mucosal integrity or motility, not attributable to T1D (i.e., recent diarrhea, gluten sensitive enteropathy, inflammatory bowel disease, irritable bowel syndrome), or current use of medications known to influence GI motility		Х	
Inability to swallow size 1 capsules. If needed, this may be verified by asking the patients to swallow one placebo capsule with water.	Х	Х	
Alcohol or illicit drug consumption, which in the opinion of the investigator, may interfere with the patient's ability to comply with the study procedures	Х	Х	
Active psychiatric problems, which in the opinion of the investigator, may interfere with the patient's ability to comply with study procedures	Х	Х	

4.4.Controlling Enrolment

Due to the design of the study, the enrolment plan, the regular MM/DSMB review and the fact that this is a multicentre study, controlling enrolment will be a critical factor for the success of this trial. Enrolment will be controlled by using the interactive web response system (Interactive Response Technology, IRT) in both Phase 1b and Phase 2a portions of this trial. All patients will require

Confidentiality Statement

registration in IRT. Details on the use of the IRT system, for registration of patients or for randomization of patients, will be outlined in the IRT manual.

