4.5. Removal of Patients

In accordance with the Declaration of Helsinki, patients have the right to withdraw from the study at any time for any reason. The Investigator and Sponsor also have the right to withdraw patients from the study. Patients may be removed from the study for the following reasons:

- Adverse reactions
- Clinical sepsis regardless of the cause
- At the request of the Investigator, MM, DSMB or Sponsor, whether for administrative or other reasons
- Protocol violation or unreliable behavior
- Termination of the study by the Sponsor

The date of and the reason for discontinuation will be recorded in the electronic case report form (eCRF).

Patients who withdraw from the study after receiving the first dose of IMP for reasons other than safety or tolerability may be replaced:

- Patients who withdraw before the Day 180 follow-up visit (primary end point) may be replaced upon consultation with the coordinating investigator and sponsor
- Patients who withdraw after the Day 180 follow-up visit will not be replaced

If a patient discontinues, all end of study visit procedures should be conducted.

If a patient is removed from the study, the date of the last dose of IMP and all observations collected up to the time of termination will be recorded on the eCRF along with the reason for termination. Scheduled safety evaluations and follow-up examinations (see Visit Schedule, Appendix A) will be conducted, if possible.

When a patient fails to return for scheduled assessments, the following efforts should at a minimum be made to contact him/her to determine a reason for the failure to return: 3 phone attempts, including the date and time, should be documented in the patient's source documents. If there is no response to the phone calls, a certified letter should be sent to the patient. After these efforts have been exhausted, a patient should be identified as lost to follow-up in the eCRF.

Patients enrolled into the Combination Cohorts who are excluded prior to receiving the first dose of IMP (teplizumab and AG019 or corresponding placebos) due to any of the criteria mentioned in Section 11.4.3.5 will be replaced. Replacement of patients will be done through the IRT. Details of this procedure are outlined in the IRT manual.

Confidentiality Statement

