 the baseline visit. The CGM device will be placed, so the patient will know how to do this at
 home. The placement of the CGM, as well as the first CGM reading, will be done prior to
 administration of the first dose of study drug(s). The Sponsor will supply the CGM devices.
- **Tuberculosis test:** As part of the eligibility verification, all patients will undergo a test to determine whether the patient shows signs of active or latent tuberculosis. The decision on the type of test to be used is left to the discretion of the investigator, and could include e.g. TST, TSPOT, QuantiFeron or other appropriate tests.
- Concomitant medications: At every visit, the investigator will obtain information about concomitant medications the patient is taking (including dose, frequency, route of administration, start and stop dates)

6.2.Safety Assessments

Safety will be assessed by collecting and recording Adverse Events (AEs) and laboratory assessments and the presence of *L. lactis* sAGX0407 in whole blood.

The study will utilize local laboratories for safety assessments. The clinical laboratory will indicate laboratory values out of normal ranges. The Investigator must assess all abnormal clinical laboratory results for clinical significance in a timely fashion. A notation of 'clinically significant' (CS) or 'non-clinically significant' (NCS) with initials and date will be documented on the respective laboratory report next to any abnormal value. An abnormal clinical laboratory value will be considered and documented as an AE, if in the opinion of the Investigator, it is clinically significant. The Investigator will follow proper adverse event reporting procedures.

For details on the data to be collected for adverse events, please refer to Section 8.

XXX

6.3.Laboratory Assessments

6.3.1General considerations

Throughout the study, blood samples will be collected at regular intervals, as described in the Visit schedule

XXX

Confidentiality Statement

XXX

6.3.2Local lab assessments

Parameters to be analysed will include:

- Hematology: complete blood count: Red Blood Cell (RBC) count, haemoglobin, haematocrit, mean corpuscular volume (MCV), mean corpuscular haemoglobin (MCH), mean corpuscular haemoglobin concentration (MCHC), RBC distribution width (RDW), white blood cell (WBC) count, differential count, platelet count
- Serum Chemistry: blood glucose, sodium, potassium, chloride, calcium, CO₂/bicarbonate

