7.2. Single Dose Patients

7.2.1Screening Visit (Day -28 – Day 0)

Following screening observations and procedures will be completed within 28 days prior to randomization:

- Signed and dated ICF
- Assessment against inclusion and exclusion criteria
- Medical history

Confidentiality Statement

- Demographic Data
- Physical Exam
- Vital signs
- 12-lead ECG
- Serum pregnancy test (in females of childbearing potential)
- Blood sampling for local lab (hematology, chemistry, specific screening blood analysis and autoantibodies testing)
- Infectious diseases (EBV, CMV, HIV, HCV, HBV)
- Tuberculosis test
- Drugs of abuse test
- Record concomitant medications
- Record adverse events
- Register patient in IRT
 - Registration in IRT should be done as soon as eligibility is confirmed and ICF is signed.
 Ideally this should be done before the Day 1 visit (start of treatment visit).

7.2.2Treatment Visit (Day 1)

Prior to the first intake of AG019, following observations and procedures will be completed:

- Register visit in IRT
- Physical Exam
- Vital Signs
- Urine pregnancy test (in women of childbearing potential)
- Record Adverse events
- Record concomitant medications
- Administer morning dose of AG019

For Single Dose patients, it is recommended to schedule the Day 1 visit on a Monday, Tuesday or Friday, to avoid having to schedule the Day 4 visit (end of study visit) on a weekend day.

7.2.3End of Study visit (Day 4)

Following observations and procedures will be completed:

- Physical exam
- Vital signs
- 12-lead ECG (only if there is suspicion of cardiac problems)
- Urine pregnancy test (in women of childbearing potential)
- Blood sampling for local lab
- Record Adverse events
- Record concomitant medications
- IMP accountability

Confidentiality Statement

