12.2. Protocol Modifications

The Sponsor may modify the protocol at any time during the life of the protocol. Protocol amendments will require IRB/IEC approval and CA approval as applicable prior to implementation except when changes to the protocol are required to eliminate immediate hazards to the study patients.

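### Protocol 4.3 waives the TB screening test for BCG-vaccinated patients, while 6.1 requires a test in every patient; align 4.3 with 6.1 and check treated patients for a missing result

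*Protocol*

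**What the plan says.** **Protocol 4.3, Exclusion Criteria.** Active or latent TB excludes a patient. The row then gives two instructions. The first covers everyone: "All patients must be evaluated for TB; including history of TB or possible previous contact with TB". The second covers the tests (TST, TSPOT, QuantiFeron or another appropriate test), which "should be performed in all patients unless vaccinated with BCG".

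**Protocol 6.1, General assessments.** As part of verifying eligibility, "all patients will undergo a test to determine whether the patient shows signs of active or latent tuberculosis". Discretion is limited to the kind of test: "The decision on the type of test to be used is left to the discretion of the investigator". BCG is not mentioned.

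**Protocol 7.2.1 and 7.3.1, screening visits.** Both list a "Tuberculosis test" with no qualifier, for single dose and repeat dose patients respectively. No later visit described in section 7 lists a TB test.

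**SAP.** TB is not among the baseline infectious diseases in section 6.3.4, which are EBV, CMV, HIV, HBV and HCV. Section 7.2 plans a protocol deviation listing (16.2.2) and, under 16.2.4, a listing of eligibility criteria not satisfied.

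**The concern.** The same screening decision is governed by two rules that differ for one group. For a BCG-vaccinated patient, 4.3 removes the test and 6.1 requires it. A site that tests everyone breaches nothing. A site that works from the eligibility table can enrol a vaccinated patient on history and contact alone.

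What is at stake is the protocol's own exclusion of latent TB. History and contact questions are not a test for it, and a vaccinated patient due to receive teplizumab could start treatment without one.

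There is also a record-keeping consequence. An untested vaccinated patient complies with 4.3 and departs from 6.1. That patient would not appear in the SAP listing of exclusion criteria met, and might or might not be recorded as a protocol deviation, depending on which section the site followed. The planned outputs would not reliably show the gap.

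**Working it through.** The plan gives no figure on this point, so the main check is a comparison of the texts, followed by a patient count.

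**1. The texts side by side**

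| Place | Who is tested | BCG exception | Weight |
|---|---|---|---|
| 4.3 | All except BCG-vaccinated patients | Yes | Eligibility rule |
| 6.1 | All patients | None | Direct requirement, same eligibility purpose |
| 7.2.1 | Test listed | None | Bare list |
| 7.3.1 | Test listed | None | Bare list |

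**2. Does silence in 6.1 mean anything?** The autoantibody requirement offers a comparison. Section 4.2 waives retesting where positivity is already documented.
- The lists in 7.2.1 and 7.3.1 include autoantibody testing without repeating that waiver. So these lists do not carry exceptions, and their silence on BCG says little.
- Section 6.3.2 does repeat the autoantibody waiver. So section 6 states a screening exception in at least that case. The lack of a BCG exception in 6.1, next to a requirement covering all patients, cannot be put down to section 6 simply omitting exceptions.

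The conflict that counts is therefore 4.3 against 6.1.

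**3. What still protects an untested vaccinated patient?**
- The history and contact evaluation in 4.3 applies to everyone.
- "Evidence of any active infection with the exception of superficial skin infections" is a separate exclusion, marked in the extracted text for the combination cohorts.
- A further 4.3 exclusion, marked for both sets of cohorts, covers medical conditions that the investigator judges could compromise safety.

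None of these requires a test for latent infection.

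**4. Planned numbers** (Protocol 3.2, 3.3 and 4.1)
- Distinct patients = single dose + new repeat dose + combination = 8 + (4 cohorts × 4) + (2 cohorts × 12) = 8 + 16 + 24 = 48. Re-enrolled single dose patients are counted once. This agrees with the maximum of 48 in 4.1.
- Teplizumab recipients = 2 cohorts × (2 open label + 10 × 4/5) = 2 × 10 = 20, of whom 10 are in the cohort aged 12 to 17.

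Both are counts before replacements, which 4.1 and 4.5 allow. The documents give neither the share of patients vaccinated with BCG nor the share of sites that follow 4.3 over 6.1, so no expected number is calculated.

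**5. Who can an amendment still reach?** SAP 4.1 describes enrolment in the past tense, and SAP 6.9 says that the second interim analysis has been done. Protocol 10.8 sets that analysis after Day 180 for all of Combination Cohort 1 and for the two open label patients of Combination Cohort 2. Section 4.5 adds: "Patients who withdraw after the Day 180 follow-up visit will not be replaced". What remains is at most replacement patients in the randomized part of Combination Cohort 2, if there are any.

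**The case against.** The strongest case on the other side has four parts.

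*The waiver may be deliberate.* It is explicit, and 6.1 can be read as a summary of an eligibility rule whose detail sits in 4.3. On that reading the cure is one edit to 6.1. This shows that the conflict can be removed in either direction, and nothing in the documents proves that the waiver was unintended. It does not remove the conflict, because 6.1 covers all patients and gives the investigator a choice of test only. Moving the waiver into 6.1 would also leave vaccinated patients untested for a condition that excludes them.

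*The support looks broader than it is.* A reader might infer that three of four places contradict 4.3. The documents do not support that weight: 7.2.1 and 7.3.1 are lists that also omit the autoantibody waiver.

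*The amendment comes late.* This stands. It is why the check of treated patients is the part with practical effect, and why that check must lead to a decision about testing. A second look at the history and contact record alone would leave the gap as it was.

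*Parts of the record are missing.* Appendix A is not supplied and could carry a footnote on BCG, and the cohort marks for the TB row are lost from the extracted text. This stands as a limit. Neither changes the wording of 4.3 or 6.1, and both refer to all patients.

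**Conclusion.** The inconsistency is real and in current text. As written, 4.3 lets a BCG-vaccinated patient enter without the test that 6.1 requires for latent TB. It is a minor point of wording with a patient-safety consequence, worth correcting because the correction adds no procedure beyond 6.1.

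The number affected is unknown and may be zero. An untested patient requires both BCG vaccination and a site that followed 4.3 over 6.1.

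A reader might draw three stronger conclusions that the documents do not support:
- **That untested patients were in fact treated.** Nothing supplied shows whether any TB result is missing.
- **That 48 and 20 cap the number concerned.** They are planned counts, and replacement after dosing is allowed.
- **That a specific TB risk with teplizumab is established.** The detail of 8.10.2 is redacted, so the point rests only on the protocol's own exclusion of latent TB.

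The TEAE primary endpoint, the analysis sets and the sample size rationale are unaffected.

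**What to change.** **1. Amend Protocol 4.3.** Replace "should be performed in all patients unless vaccinated with BCG" with a statement that a test must be performed in every patient. Keep the list of acceptable tests and the investigator's choice among them. Sections 6.1, 7.2.1 and 7.3.1 need no change.

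*Cost:* one phrase, but a formal amendment: "Protocol amendments will require IRB/IEC approval and CA approval as applicable prior to implementation". It adds one test per vaccinated patient at the existing screening visit, which 6.1 already requires. Its reach is limited to replacement patients, if any.

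**2. Check patients already treated.** Identify any without a TB test result and list them as deviations from 6.1 in SAP listing 16.2.2, so that classification does not vary by site. The medical monitor then decides for each, teplizumab recipients first, whether the test that 6.1 required should now be done, and records the decision.

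*Cost:* a review of 48 planned patients plus any replacements. No supplied text shows that the TB result is captured in the eCRF, so it may have to be collected from source documents.
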